Study Design

This is a single arm, open label, prospective study evaluating the safety and clinical efficacy of the combination of nivolumab, ipilimumab and hypofractionated palliative radiation therapy (SBRT) in patients with advanced salivary gland cancer.

Patients enrolled will receive the following treatment (see Section 5.1.1):

1. Nivolumab 3mg/kg IV Q 2 weeks x 12 doses followed by Nivolumab 480 mg IV Q4 weeks x 8 doses
2. Ipilimumab 1 mg/kg IV Q6 weeks x 4 doses
3. Hypofractionated radiation therapy (SBRT) given to a total dose of 24Gy given in 3 fractions every other day over 1 week and initiated 2 weeks after the first dose of nivolumab and ipilimumab. The target lesion will be a local/regional or metastatic disease site that per the multidisciplinary head and neck team, requires local control for palliation and/or prevention of impending symptoms.

Both nivolumab and ipilimumab have well established toxicity profiles as a single agent and in combination. However, since the combination of nivolumab, ipilimumab and palliative radiation has not previously been described or studied, the first 6 patients who will be enrolled in this study will represent the initial safety run-in phase. Patients will receive full dose nivolumab and ipilimumab. Enrollment will be halted until these first 6 patients complete the first 12 weeks of treatment and acute toxicities will be reviewed. If more than 2 DLTs (to be defined in Section 5.1.2) are noted in this 6 patient cohort, a dose modification will be implemented (Section 5.1.1) for the remaining 14 patients who will be enrolled in the expansion cohort. Enrollment period is 24 months and duration of the trial 48 months.

Study Population

The study aims to enroll patients with salivary gland carcinomas (WHO, 2005), who are not candidates for curative intent therapy and who have a target lesion (either local/regional or distant metastatic site involving the lung and/or bone), that requires local control for palliation, as determined by a multidisciplinary team.

Inclusion Criteria:

1. Histologically proven salivary gland carcinoma (WHO, 2005) arising from a previous head and neck primary site, and located within the head and neck region, lung or bone, and who are not candidates for curative intent therapy.
2. ≥ 18 years old at the time of signing informed consent.

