4.2 Study Schema

Note: refer to Dosing and Administration (Section 5.1.1) for further details on treatment scenarios.

Clinical Study Protocol RG1718030
Drug Substance: Nivolumab and Ipilimumab
IND Number:140818
Protocol version 3.0 April 17, 2019

Both ipilimumab and nivolumab are FDA approved, and the safety profile of both agents have been extensively studied. However, because the combination with radiation has not been previously studied, the first 6 patients of this study will represent the initial run-in phase of the triplet combination of nivolumab, ipilimumab and palliative radiation. The initial doses of ipilimumab and nivolumab will be administered on day 1 of therapy.

Stereotactic radiation will be initiated on Week 3 of treatment. SBRT will be delivered to a total dose of 24 Gy, given in 3 fractions of 8Gy every other day. Treatment will be continued according to the study schema unless patient withdraws consent, has confirmed disease progression, and/or develops toxicity that results in treatment discontinuation.

Enrollment will be halted until these first 6 patients complete the first 12 weeks of treatment and acute toxicities will be reviewed. If more than 2 DLTs (to be defined in Section 5.1.2) are noted in this six patient cohort, a dose modification will be implemented (Section 5.1.1) for the remaining 14 patients who will be enrolled in the expansion cohort.

Serum correlative studies will be collected at the following timepoints: at baseline, prior to week 8, and prior to week 16 of treatment. Archived formalin fixed paraffin embedded tissue (obtained in the 12 months prior to trial enrollment) will be collected from patients enrolled. If the patient does not have archived tissue available, a fresh biopsy will be obtained. Tissue requirement will be waived if deemed contraindicated or not clinically available/accessible for resection per the treating physician (PI approval required).

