5. TREATMENT

5.1 Systemic Therapy

5.1.1 Dosage and Administration

The treatment to be used in the run-in phase (initial 6 patients) of this trial is outlined in the table below. If ≤ 1 DLT is observed in the run-in phase, then the remaining 14 patients will be provided treatment per the following:

Drugs	Dose/Potency	Dose Frequency	Route of Administration	Regimen/Treatment Period
Weeks 1-24				
1. Nivolumab	3 mg/kg	Q2 weeks	IV infusion	Maximum of 12 doses
2. Ipilimumab	1mg/kg	Q6 weeks	IV infusion	Maximum of 4 doses
Weeks 25-52				
1. Nivolumab	480mg IV flat dose	Q4 weeks	IV infusion	Maximum of 8 doses

If 2 or more DLTs (defined in Section 5.1.2) are observed in the run-in phase, the following treatment will be used for the remaining 14 patients to be treated on the clinical trial protocol:

Drugs	Dose/Potency	Dose Frequency	Route of Administration	Regimen/Treatment Period
Weeks 1-24				
1. Nivolumab	3 mg/kg	Q4 weeks	IV infusion	Maximum of 6 doses
2. Ipilimumab	1mg/kg	Q8 weeks	IV infusion	Maximum of 3 doses
Weeks 25-52				
1. Nivolumab	480mg IV flat dose	Q6 weeks	IV infusion	Maximum of 4 doses

Patients who experience a DLT in the run-in phase, will have dose interruptions/reductions as outlined in Section 5.1.3.

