5.1.2 Definition of DLT

Dose-limiting toxicities (DLTs) will be evaluated during the run-in phase consisting of the first 6 patients enrolled in this trial. The period for evaluating DLTs will be from the time of first administration of nivolumab and ipilimumab until 12 weeks. Adverse event monitoring will continue for these subjects throughout the course of their treatment as outlined in the Schedule of Study Assessments, these adverse events will include potential XRT related toxicities. Subjects who do not remain on the study up to this time for reasons other than DLT will be replaced with another subject. Grading of DLTs will follow the guidelines provided in the Common Terminology Criteria for Adverse Events (CTCAE) version 5.0.

A DLT will be defined as any Grade 3 or higher toxicity that occurs during the DLT evaluation period. Toxicity that is clearly and directly related to the primary disease or to another etiology is excluded from this definition. The following will be DLTs:

- Any Grade 4 irAE
- Any \geq Grade 3 colitis
- Any Grade 3 or 4 noninfectious pneumonitis irrespective of duration

- Any Grade 2 pneumonitis that does not resolve to \leq Grade 1 within 3 days of the initiation of maximal supportive care
- Any Grade 3 irAE, excluding colitis or pneumonitis, that does not downgrade to Grade 2 within 3 days after onset of the event despite optimal medical management including systemic corticosteroids or does not downgrade to \leq Grade 1 or baseline within 14 days
- Liver transaminase elevation $> 8 \times$ ULN or total bilirubin $> 5 \times$ ULN
- Any \geq Grade 3 non-irAE, except for the exclusions listed below
 - Grade 3 fatigue lasting \leq 7 days
 - Grade 3 endocrine disorder (thyroid, pituitary, and/or adrenal insufficiency) that is managed with or without systemic corticosteroid therapy and/or hormone replacement therapy and the subject is asymptomatic
 - Grade 3 inflammatory reaction attributed to a local antitumor response (e.g., inflammatory reaction at sites of metastatic disease, lymph nodes, etc.)
 - Concurrent vitiligo or alopecia of any AE grade
 - Grade 3 infusion-related reaction (first occurrence and in the absence of steroid prophylaxis) that resolves within 6 hours with appropriate clinical management

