 - Grade 3 or 4 neutropenia that is not associated with fever or systemic infection that improves by at least 1 grade within 3 days. Grade 3 or Grade 4 febrile neutropenia will be a DLT regardless of duration or reversibility
 - Grade 3 or 4 lymphopenia
 - Grade 3 thrombocytopenia that is not associated with clinically significant bleeding that requires medical intervention, and improves by at least 1 grade within 3 days
 - Isolated Grade 3 electrolyte abnormalities that are not associated with clinical signs or symptoms and are reversed with appropriate maximal medical intervention within 3 days
- Grade 4 hematologic toxicity, not described in exclusions above
- Prolonged delay (>2 weeks) in initiating second dose of nivolumab or ipilimumab due to treatment-related toxicity
- Grade 5 toxicity, i.e., death

Dose modification/delays according to Section 5.1.3 will apply to the patients who experience DLTs in the run-in phase.

Immune-related AEs are defined as AEs of an immune nature (i.e., inflammatory) in the absence of a clear alternative etiology. In the absence of a clinically significant abnormality, repeat laboratory testing will be conducted to confirm significant laboratory findings prior to designation as a DLT.

During this DLT period, patients who received <90% of the nivolumab OR ipilimumab infusion on day 1 (e.g., because the infusion of either drug had to be discontinued due to an infusion reaction) and did not experience a DLT will not be taken into account in the assessment of the overall DLT rate for the phase I run-in cohort and will be replaced.

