8.4 STUDY STOPPING RULE

In keeping with the study primary endpoint, a stopping rule will be implemented in the unlikely event that the combination under study is deemed to have unacceptably high toxicities. Enrollment will be halted if more than 3 patients experience a Grade 4 or higher drug related toxicity (CTCAE v. 5) during the trial treatment period or up to 30 days after the last investigational drug infusion. The likelihood of observing more than 3 Grade 4+ drug-related adverse events is 80% if the true

rate is 20% and the likelihood is 91% if the true rate is 25%. This rule has an 83% chance of prematurely discontinuing trial enrollment after the 1st 10 patients are enrolled if the true rate of Grade 4 drug related toxicity is 40%. The study will be reviewed by the University of Washington/Fred Hutch Cancer Consortium Data and Safety Monitoring Committee (DSMC

STATISTICAL CONSIDERATIONS

All patients enrolled in the study, including those in the run-in phase will be included in the analysis of toxicity and efficacy.

Safety and tolerability is the primary endpoint of this study, and all patients enrolled will be assessed for this endpoint. Adverse events will be recorded and graded based on CTCAE v. 5, and their relationship to the experimental agents reported.

Similarly, all patients enrolled in the study (i.e., the initial 6 patient cohort, and the additional 14 patient expansion) will be included in the efficacy analyses. Clinical responses to the combination of nivolumab, ipilimumab and hypofractionated radiation will be based on RECIST 1.1 criteria. Oncologic outcome endpoints such as progression free and overall survival will be calculated from the date of study enrollment, until disease progression or death from any cause, respectively. Survival estimates will be calculated using the Kaplan-Meier method.

Exploratory endpoints of this study include correlative work performed on research serum and tissue samples.

Sample size determination

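### In the supplied text no rule pauses enrolment after a treatment-related death: section 8.4 counts a drug-related death like a Grade 4 event and acts only when more than 3 patients are affected

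*Combined protocol and SAP*

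**What the plan says.** **Trial-wide rule.** Section 8.4 (Study Stopping Rule) reads "Enrollment will be halted if more than 3 patients experience a Grade 4 or higher drug related toxicity (CTCAE v. 5", over the treatment period and up to 30 days after the last infusion. It gives probabilities of meeting the rule of 80% and 91% at true rates of 20% and 25%, and 83% within the first 10 patients at 40%. The section ends on "The study will be reviewed by the University of Washington/Fred Hutch Cancer Consortium Data and Safety Monitoring Committee (DSMC", where the text breaks off.

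**Run-in.** Section 4.2 states: "Enrollment will be halted until these first 6 patients complete the first 12 weeks of treatment and acute toxicities will be reviewed". The DLT definition in 5.1.2 is not confined to drug-related events ("A DLT will be defined as any Grade 3 or higher toxicity that occurs during the DLT evaluation period", less toxicity clearly due to the disease or another cause). Monitoring of these patients extends to radiation: "these adverse events will include potential XRT related toxicities". Death is one item in the DLT list ("Grade 5 toxicity, i.e., death"). Section 5.1.1 then says: "If ≤ 1 DLT is observed in the run-in phase, then the remaining 14 patients will be provided treatment per the following", and the table that follows is the unchanged schedule. Two or more DLTs change the schedule. The synopsis and 4.2 set that cut-off at more than 2.

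**Other safeguards.** Section 8 requires SAEs, related or not, to reach the drug supplier within 24 hours. An SAE that may stem from a study procedure has that relationship recorded in the report narrative. The Related/Not related scale in 8.2 refers to study drug only. The study team reviews adverse events weekly (section 3). The DSMC, SRC and IRB review as needed, and their approval is necessary to continue (section 9, Monitoring of the study).

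**The concern.** Safety is the primary endpoint, and section 4.2 says the combination with radiation has not been studied before. In such a trial one would expect a single treatment-related death to stop new entries until an independent body has looked at it. The only event-triggered rule in the supplied text instead treats that death as one of four events needed to halt.

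Two accrual windows are affected: entry of patients 2 to 6, for which no stagger is stated, and the 14-patient expansion, which has no further scheduled hold. In either window the written rules allow the next patient to start the same triplet before a related death has had a required review. The gap is wider for radiation, the new component, because 8.4 counts drug-related events only.

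**Working it through.** **1. Which threshold do the printed figures fit?** Exact binomial tail, P(X ≥ r), with X ~ Bin(n, p):

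| n, true rate | Printed in 8.4 | r = 4 (more than 3) | r = 3 (3 or more) |
|---|---|---|---|
| 20, 20% | 80% | 58.9% | 79.4% |
| 20, 25% | 91% | 77.5% | 90.9% |
| 10, 40% | 83% | 61.8% | 83.3% |

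The wording acts at the fourth patient; the figures belong to a rule acting at the third. That mismatch is a separate error, so both readings are carried below. On neither does a first or second death alone halt enrolment.

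**2. Does 8.4 protect the run-in?** P(4 or more of 6 patients with Grade 4+) is 1.7% at a 20% rate and 3.8% at 25%. It rarely acts that early.

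**3. Death by the end of the trial with 8.4 never met (exact).** Let t be the total drug-related Grade 4+ rate, d the drug-related death rate (part of t) and L the largest count that does not trigger (3 or 2). The documents give no death rate; d = 1%, 2% and 5% are assumptions, and t = 20% and 25% are the rates used in 8.4.

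P = P(Bin(20, t) ≤ L) − Σ_{j=0..L} C(20, j)(t − d)^j (1 − t)^(20−j)

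For t = 0.20, d = 0.02, L = 3: 0.411 − 0.324 = 0.087. For d = 1%, 2%, 5%:
- t = 20%: 5%, 9%, 19% (more than 3); 2%, 3%, 7% (3 or more).
- t = 25%: 2%, 4%, 9% (more than 3); 1%, 1%, 3% (3 or more).

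Some of these deaths would fall after accrual has ended.

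**4. Further entries after a death while 8.4 is unmet (simulation).** The synopsis states: "Enrollment period is 24 months and duration of the trial 48 months". Entries are evenly spaced with a 12-week hold between patients 6 and 7; over 24 months the spacing is (104 − 12)/18 = 5.11 weeks. A 12-month accrual is the sensitivity case. Event times are uniform from entry, over either 12 weeks or 56.3 weeks (52 weeks plus 30 days). Counted are entries of patients 2 to 6 after a first death, and entries of patients 8 to 20 after a first death that follows patient 7's entry, in both cases before the triggering Grade 4+ patient. Entries that follow the scheduled review are thus not blamed on deaths that review would have seen. The table gives the chance of at least one such entry for d = 1% / 2% / 5%; ranges span the two event-time assumptions.

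| t, accrual | More than 3 | 3 or more |
|---|---|---|
| 20%, 24 months | 10-11% / 19-21% / 42-46% | 7-8% / 14-15% / 33-36% |
| 20%, 12 months | 6-9% / 13-18% / 29-40% | 5-6% / 11-12% / 25-29% |
| 25%, 24 months | 9% / 17-18% / 38-40% | 6% / 12% / 28-30% |
| 25%, 12 months | 6-8% / 12-15% / 28-34% | 5% / 9-10% / 23-24% |

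When it happens, the median number of further entries is 3 to 6 (more than 3) or 3 to 5 (3 or more). These chances exceed those in step 3 because 8.4 may be met only after the entries have occurred. For patients 2 to 6 alone (t = 20%, 24 months, more than 3) the chances are 1-4%, 3-8% and 7-20%; the ceiling 1 − (1 − d)^5 is 5%, 10% and 23%.

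**5. A single fatal DLT in the run-in.** With an assumed non-fatal DLT rate q, the chance that exactly one of six patients has a DLT and that it is fatal is 6·d·(1 − q − d)^5. This gives 2%, 3%, 7% for q = 20% and 1%, 2%, 3% for q = 30%. On either run-in cut-off (5.1.1, or the synopsis and 4.2) the schedule then stays unchanged.

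**The case against.** The strongest reply is that absence cannot be established from this text. A death rule would naturally sit in the DSMC sentence of 8.4, which is cut off, or in the institutional Data and Safety Monitoring Plan, which section 9 invokes but which is not supplied. That stands, and it limits the point to what is visible.

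Second, a death has many routes to review: 24-hour SAE reporting, weekly team meetings, IRB and health-authority reporting, the supplier's expedited safety reports, and committees whose approval is needed to continue. A fatal DLT within 12 weeks in the run-in would also be looked at before patient 7. Procedure-related SAEs, which would plausibly include an SBRT death, already have that relationship recorded. All of this is correct. These routes could lead to a pause, but none in the supplied text requires one.

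Third, the sizes rest on assumed death rates and fall with faster accrual or a higher Grade 4+ rate. That also stands, which is why ranges are given. A 10% death rate is left out: within a 20% Grade 4+ rate it would make half of all such patients' events fatal, and nothing in the documents supports that.

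A reader might infer that deaths would go unreviewed, or that continuing accrual is left wholly to ad hoc judgement. The documents do not support either inference, given the safeguards above and the missing monitoring text.

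**Conclusion.** The point holds as a gap in the visible rules. Following section 8.4 as written, accrual to a new triplet may continue after one, two or three drug-related deaths if no other patient has a Grade 4+ event (one or two under the 3-or-more reading). A death attributed only to SBRT never enters the count.

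Across Grade 4+ rates of 20-25% and accrual over 12-24 months, the chance that at least one further patient is entered after a drug-related death while 8.4 is unmet is about 6-11%, 12-21% and 28-46% as worded. Under 3 or more it is about 5-8%, 9-15% and 23-36%. These correspond to assumed death rates of 1%, 2% and 5%, and they measure how often no written rule acts. The gap itself does not depend on these rates.

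Confidence is medium, because the monitoring plan and the rest of the DSMC sentence could already close it. This is a design choice worth improving. It does not invalidate the analysis.

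**What to change.** Add to section 8.4, as a limb separate from the Grade 4+ count: any Grade 5 event judged related to nivolumab, ipilimumab or SBRT pauses new enrolment until the Consortium DSMC has reviewed it and agreed that enrolment may resume. For SBRT, use the study-procedure relationship that section 8 already has recorded in the SAE report.

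Optionally, cross-refer from 5.1.1 so that a fatal run-in DLT needs DSMC agreement before the remaining 14 patients receive the unchanged schedule.

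If the institutional monitoring plan already requires such a pause, citing it in 8.4 is enough.

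This is a cheap improvement: one sentence and perhaps one cross-reference, using a committee already in place. Sample size, the Grade 4+ rule and the analysis are unchanged. The downside is a short accrual pause if a related death occurs.

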4. INVESTIGATIONAL PLAN/STUDY DESIGN

4.1 Study Design Overview

This study will be carried out as a single institution, single arm phase I/II unblinded trial. A maximum of 20 patients will be enrolled. Each patient will be treated with nivolumab, ipilimumab and stereotactic body radiation therapy. Nivolumab will be continued for a total of 12 cycles, unless evidence of unacceptable toxicity, disease progression or withdrawal of patient consent were to occur.

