There are multiple ongoing studies in various tumor types exploring the activity of nivolumab and ipilimumab. In a published report of the combination in patients with advanced NSCLC treated on a phase I study (Checkmate, 012), treatment related serious adverse events were observed in 28% of patients (Hellmann Lancet Oncol 2017). This study plans to accrue 20 patients, a sample size that would allow us to estimate grade 3 or higher acute drug related toxicity rate of 30% with a confidence interval of 20% (95% confidence level) or an upper bound of 50%. This would allow us to reasonably exclude a clinically significant increase in toxicity with the addition of radiation therapy to the nivolumab and ipilimumab combination as defined by the upper bound of the confidence interval.

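### The stopping rule in Section 8.4 halts at more than 3 patients, but its stated probabilities (80%, 91%, 83%) are those of a rule that halts at 3 or more

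*Combined protocol and SAP*

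**What the plan says.** Section 8.4 (Study Stopping Rule) sets the boundary: "Enrollment will be halted if more than 3 patients experience a Grade 4 or higher drug related toxicity", counted during the treatment period or up to 30 days after the last infusion. Its performance is then given in two sentences.

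- The first reads "The likelihood of observing more than 3 Grade 4+ drug-related adverse events is 80% if the true" and continues "rate is 20% and the likelihood is 91% if the true rate is 25" per cent.
- The second reads "This rule has an 83% chance of prematurely discontinuing trial enrollment after the 1st 10 patients are enrolled", with the condition "if the true rate of Grade 4 drug related toxicity is 40" per cent.

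The first of these sentences gives no number of patients. Two other places supply one. The sample size paragraph says "This study plans to accrue 20 patients", and Section 4.1 says "A maximum of 20 patients will be enrolled". No other part of the document restates the boundary or gives other operating characteristics.

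**The concern.** More than 3 patients means 4 or more. With 20 patients and a true rate of 20%, the expected number with an event is 20 × 0.20 = 4. A boundary that sits at the expected count should be reached only somewhat more than half the time, so a stated 80% looks too high. The other two figures look too high in the same way.

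Safety is the primary endpoint, and the protocol says that the triplet with radiation has not been studied before. Section 3 has the scientific review committee and the IRB approve the protocol, and Section 9 has the review committees evaluate stopping rules. If the percentages do not belong to the written boundary, those bodies have judged the rule on a performance that it does not have. The text also leaves open what the designers meant to happen at the third affected patient: the wording says continue, while the calculation assumes a halt.

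**Working it through.** **Inputs.** The boundary, the true rates of 20%, 25% and 40%, and n = 10 for the third figure come from Section 8.4. For the first two figures n is not stated there. I take n = 20, the planned and maximum enrollment in the sample size paragraph and Section 4.1.

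**Formula.** Let X be the number of patients with a qualifying toxicity, binomial with parameters n and p. The chance of reaching a boundary of r patients is

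P(X ≥ r) = 1 − Σ C(n,k) p^k (1−p)^(n−k), summed over k = 0 to r − 1.

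**Step 1: reproduce the plan's figures.** They come out with r = 3:

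- n = 20, p = 0.20: 0.7939 (stated 80%)
- n = 20, p = 0.25: 0.9087 (stated 91%)
- n = 10, p = 0.40: 0.8327 (stated 83%)

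**Step 2: apply the rule as written.** More than 3 is r = 4, so the term for exactly 3 patients is removed:

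- n = 20, p = 0.20: C(20,3) × 0.20³ × 0.80¹⁷ = 0.2054, and 0.7939 − 0.2054 ≈ 0.5886 before rounding of the terms
- n = 20, p = 0.25: C(20,3) × 0.25³ × 0.75¹⁷ = 0.1339, and 0.9087 − 0.1339 = 0.7748
- n = 10, p = 0.40: C(10,3) × 0.40³ × 0.60⁷ = 0.2150, and 0.8327 − 0.2150 = 0.6177

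**Step 3: compare.**

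| Setting | Stated | 4 or more (as written) | 3 or more | Stated minus as written |
|---|---|---|---|---|
| n = 20, 20% | 80% | 58.9% | 79.4% | 21.1 points |
| n = 20, 25% | 91% | 77.5% | 90.9% | 13.5 points |
| n = 10, 40% | 83% | 61.8% | 83.3% | 21.2 points |

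**Step 4: look for another explanation.**

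- Neighbouring boundaries do not fit. 2 or more gives 93.1%, 97.6% and 95.4%; 5 or more gives 37.0%, 58.5% and 36.7%.
- Approximations to the written rule do not fit. The Poisson gives 56.7%, 73.5% and 56.7%; the continuity-corrected normal gives 61.0%, 78.1% and 62.7%.
- A different n does not fit. Among n from 14 to 35, with 4 or more, only n = 26 brings both of the first two figures within 2 points (79.3% and 92.0%). That exceeds the maximum of 20, and the third figure, whose n is stated, would still be 61.8%.

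**The case against.** The arithmetic is not in dispute, but several points bear on how much it matters.

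**The written rule delays more than it misses.** At a true 40% rate, 38.2% is the chance that the rule has not yet triggered by patient 10. By patient 20 it has triggered with probability 98.4%. If each outcome were known at once, mean enrollment at 20%, 25% and 40% would be 16.5, 14.6 and 9.9 patients under more than 3, against 13.6, 11.5 and 7.5 under 3 or more. The average difference is thus about 2.5 to 3 patients. This stands as a measure of the practical effect. It does not make the stated percentages right.

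**All these figures are idealised.** The toxicity window runs through treatment and 30 days beyond, so some events will be known only after later patients have enrolled. The toxicity rate may also change if the run-in leads to a modified schedule. This is fair, but the plan's own figures carry the same simplification, and delayed events would make early stopping less likely still.

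**The probability sentence counts events, not patients.** Several events in one patient could raise an event count. However, the documents give no model of events per patient, and a simple per-patient binomial with 3 or more fits all three figures.

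**Other safeguards exist.** Enrollment pauses after 6 patients for a 12-week review of dose-limiting toxicities, and committees review adverse events. But the run-in rule covers only those 6 patients and leads to a dose modification, while the committee review described in Section 9 is as needed. Neither repairs the numbers in Section 8.4.

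**The instruction itself is clear.** More than 3 appears in both the rule and the probability sentence, so staff would apply it consistently. That is so, and the documents do not show whether the boundary or the percentages carry the error. The case for correction rests on the two being incompatible.

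**Conclusion.** The concern holds. The boundary and its stated operating characteristics cannot both be right. All three percentages fit 3 or more patients to within a percentage point, and none fits the written rule, so this is an off-by-one error and not rounding. The only loose fit is 79.4%, which rounds to 79% where the plan states 80%.

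As written, the rule triggers with probability 58.9% at a true 20% rate and 77.5% at 25% over 20 patients, and 61.8% at 40% within the first 10. The corresponding chances of not triggering are 41.1%, 22.5% and 38.2%, where the text implies 20%, 9% and 17%.

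The calculation assumes independent patients, one constant rate and outcomes known when the rule is applied. The first two figures also assume n = 20. The third does not, and it shows the same error. Because this is a safety threshold in a trial whose primary endpoint is safety, the paragraph must be corrected.

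**What to change.** Reconcile the rule and the figures in Section 8.4 by one of two routes. The choice belongs to the investigators and the review committees.

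- Keep more than 3 patients, and restate the probabilities as 59%, 78% and 62%.
- State the rule as 3 or more patients, and give the probabilities as 79%, 91% and 83%.

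Under either route, count patients in both the rule and the probability sentences, give n for every probability (20, 20 and 10), and say that the figures assume each patient's outcome is known when the rule is applied.

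It would also help, though it is not needed to correct the error, to add the chance of halting at a rate the investigators would find acceptable. The plan names no such rate. At an illustrative 10% with n = 20, the chance is 13.3% under more than 3 and 32.3% under 3 or more, so the choice matters at low rates as well.

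The cost is one paragraph in a protocol amendment, with no added patients or procedures. The first route makes the stated performance less favourable; the second makes a halt somewhat more likely.
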